#### 4.1. Protocol Deviations

Important protocol deviations (including deviations related to study inclusion/exclusion criteria, conduct of the trial, patient management or patient assessment) will be summarised and listed.

Protocol deviations will be tracked by the study team throughout the conduct of the study in accordance with the Protocol Deviation Management Plan [13Apr2020 V5.0].

- Data will be reviewed prior to freezing the database to ensure all important deviations and deviations which may lead to exclusion from the analysis are captured and categorised on the protocol deviations dataset.
- This dataset will be the basis for the summaries and listings of protocol deviations.

A separate summary and listing of all inclusion/exclusion criteria deviations will also be provided. This summary will be based on data as recorded on the inclusion/exclusion page of the eCRF.

CONFIDENTIAL

205665

## 5. CONSIDERATIONS FOR DATA ANALYSES AND DATA HANDLING CONVENTIONS

### 5.1. Study Treatment & Sub-group Display Descriptors

Treatment Group Descriptions			
[RandAll NG / FSO Randomization System]		Data Displays for Reporting	
Code	Description	Description	Order in TLF
A	IV epoetin alfa	rhEPO	2
B	Daprodustat	Dapro	1
-	-	Total	3

Treatment comparisons will be displayed as follows using the descriptors as specified:

Dapro vs rhEPO

Within each treatment group/arm, the display descriptors for the study periods/visits will be as follows:

Pre-Protocol Amendment 3	Post-Protocol Amendment 3
Study Period (Visit)	Study Period (Visit)
Screening* (Week -8 to Week -4)	Screening* (7-30 days prior to Week -2)
ESA Washout* (Week -4 to Day 1)	ESA Washout* (Week -2 to Day 1)
Acute Challenge 1 (Day 1)	Acute Challenge 1 (Day 1)
Hgb Maintenance Phase (Day 2 to Day 56)	Hgb Maintenance Phase (Day 2 to Day 56)
Acute Challenge 2 (Day 57)	Acute Challenge 2 (Day 57)
Hgb Maintenance Phase (Day 58 to day before repeated AC2)	Hgb Maintenance Phase (Day 58 to day before repeated AC2)
Repeat Acute Challenge 2**	Repeat Acute Challenge 2**
Early Withdrawal	Early Withdrawal
Follow-up (Day 58 to Week 10)	Follow-up (Day 58 to Week 10)

\*For these visits, the period will include the first visit up to but not including the last reference visit. For example, screening period for pre-protocol amendment 3 will be defined as week -8 up to but not including the week -4 visit.

CONFIDENTIAL

205665

\*\*For subjects with a repeat acute challenge 2, the follow-up period will be the day following this visit

## 5.2. Baseline Definitions and Derivations

### 5.2.1. Baseline Definitions

For all endpoints the baseline value will be the latest non-missing pre-dose assessment before Acute Challenge 1 as detailed in the following table. Pre-dose values following Acute Challenge 1 following the maintenance therapy will not be used as baseline.

Parameter	Study Assessments Considered As Baseline			Baseline Used in Data Display
	Screening	Week -2	Day 1 (Pre-Dose)	
Pre-Acute Challenge 1				
ABPM Parameters			X	Post-HD/Pre-Acute Challenge 1
Vital signs (SBP, DBP and pulse rate)	X	X	X (post-HD)	Post-HD and Pre-Acute Challenge 1
Laboratory data	X		X	Day 1(Pre-dose)
ECG	X		X	Day 1(Pre-dose)
Biomarkers			X	Day 1(Pre-dose)
NOTES: Unless otherwise stated, the mean of replicate assessments at any given time point will be used as the value for that time point.				

### 5.2.2. Derivations and Handling of Missing Baseline Data

Unless otherwise stated, if baseline data is missing no derivation will be performed and baseline will be set to missing.

#### *Change from Baseline*

Definition	Reporting Details
Change from Baseline	= Post-Dose Visit Value – Baseline

#### **NOTES:**

- Unless otherwise specified, the baseline definitions specified in Section 5.2.1 Baseline Definitions will be used for derivations for endpoints / parameters and indicated on summaries and listings.
- Unless otherwise stated, if baseline data is missing no derivation will be performed and the change from baseline value will be set to missing.
- The baseline definition will be footnoted on all change from baseline displays.

#### *Percent Change from Baseline*

Ferritin and serum iron will be log-transformed. Instead of reporting change from baseline and mean, percent change from baseline and geometric mean will be reported.

**CONFIDENTIAL**

205665

To calculate a geometric mean for baseline measurement or at a specified timepoint, the following steps are used:

1. Log-transform the data points
2. Calculate the mean and standard error (SE) of the log-transformed data
3. Exponentiate the mean, (if required, the mean – SE, mean + SE) and the endpoints of the confidence interval back to the original scale in order to obtain the geometric mean, (the geometric mean – SE, the geometric mean + SE) and the confidence interval for the geometric mean.
4. Coefficient of variation will be calculated as

$$CV = \sqrt{\exp(\text{Var}_{\log\text{scale}}) - 1} \times 100\%$$

To calculate a geometric mean for the ratio of a specific timepoint to baseline (expressed as a percent change from baseline), the following steps are used:

1. Log-transform the data at both the baseline and the specified timepoint
2. For each participant, calculate a change from baseline using the log-transformed data
3. Calculate the mean and standard error (SE) of the log-transformed data
4. Exponentiate the mean, (if required, the mean – SE, the mean + SE) and the endpoints of the confidence interval, back to the original scale and then subtract 1, then multiply everything by 100% in order to express the geometric mean, (the geometric mean – SE, the geometric mean + SE) and the confidence interval (CI) as the percent change from baseline.

Geometric mean for percent change from baseline =

$$[ \text{Exp}(\sum \{ \log(\text{value at specified time point}_i) - \log(\text{baseline value}_i) \} / n) - 1 ] \times 100,$$

Where  $i$  = participant,  $n$  = total number of participants, and  $\sum$  represents the sum over all participants.

To calculate the minimum, median and maximum for the ratio of a specific timepoint to baseline (expressed as a percent change from baseline), the following steps are used:

1. Log-transform the data at both the baseline and the specified timepoint
2. For each participant, calculate a change from baseline using the log-transformed data
3. Calculate the minimum (median and maximum) of change from baseline using the log transformed data.
4. Exponentiate the minimum (median and maximum), back to the original scale and then subtract 1, then multiply everything by 100% in order to express the minimum (median and maximum) as the percent change from baseline.

Minimum percent change from baseline =

$$[ \text{Exp}(\min \{ \log(\text{value at specified time point}_i) - \log(\text{baseline value}_i) \}) - 1 ] \times 100,$$

Where  $i$  = participant.

**CONFIDENTIAL**

205665

Unless otherwise specified, the baseline definitions specified in Section 5.2.1 will be used for derivations for endpoints/parameters and indicated on summaries and listings. Unless otherwise specified, if baseline data is missing, no derivation will be performed and the % change from baseline value will be set to missing.

### 5.3. Multicentre Studies

In this multicentre study, enrolment will be presented by investigative site.

### 5.4. Examination of Covariates, Other Strata and Subgroups

#### 5.4.1. Covariates and Other Strata

The list of covariates and other strata may be used in descriptive summaries and statistical analyses, some of which may also be used for subgroup analyses. Additional covariates and other strata of clinical interest may also be considered.

Category	Details
Strata	Prior treatment by ESA Dose (low ESA/high ESA)
Covariates	Treatment (daprodustat/epoetin alfa)
	Post_HD/pre-Acute Challenge 1 BP (SBP, DBP, MAP, HR)
	Difference in SBP between post-HD/pre-Acute Challenge 2 BP (SBP, DBP, MAP, HR) and post-HD/pre-Acute Challenge 1.

The pre-challenge SBP may change over time between Acute Challenge 1 and Acute Challenge 2 as a result of the maintenance therapy, and thus the pre-challenge SBP at Acute Challenge 2 is not a true pre-treatment covariate. Therefore, pre-Acute Challenge 2 SBP will not be used as a covariate. Instead, any impact on the SBP due to the covariate between Challenge 1 to Challenge 2 will be adjusted for using the covariate ‘Difference in SBP between post-HD/pre-Acute Challenge 2 SBP and post-HD/pre-Acute Challenge 1’.

The primary model will include the interaction between treatment and ‘difference in post-HD SBP between Acute Challenge 1 and 2’. As a result, the interpretation of the effect of the Acute Challenge 2 may be confounded by the impact of treatment phase on the covariate. Therefore, if the interaction term in this model is significant at the 0.10 level, then the primary model will be ANCOVA with terms for treatment, post-HD/pre-Acute Challenge 1 SBP, and prior ESA dose (low/high).

Stratification factor (previous ESA dose) will be used as a fixed factor in the model where indicated in Section 11. See details below:

Classification Name (Description)	Value	Code/Range
Treatment by ESA Dose (Treatment by Previous ESA Dose)	Low ESA Dose	1
	High ESA Dose	2

#### 5.4.2. Examination of Subgroups

No subgroups will be examined.

#### 5.5. Multiple Comparisons and Multiplicity

No multiplicity adjustments will be made for the final analysis of the secondary endpoints. Although the secondary and exploratory analyses will include statistical testing, these will be considered as exploratory and no Type I error adjustments will be made.

#### 5.6. Other Considerations for Data Analyses and Data Handling Conventions

Other considerations for data analyses and data handling conventions are outlined in the appendices:

Section	Component
14.3	Appendix 3: Assessment Windows
14.4	Appendix 4: Study Phases and Treatment Emergent Adverse Events
14.5	Appendix 5: Data Display Standards & Handling Conventions
14.6	Appendix 6: Derived and Transformed Data
14.7	Appendix 7: Reporting Standards for Missing Data
14.8	Appendix 8: Values of Potential Clinical Importance

## 6. STUDY POPULATION ANALYSES

### 6.1. Overview of Planned Study Population Analyses

The study population analyses will be based on the ITT population unless otherwise specified.

Study population analyses including analyses of participant's disposition, protocol deviations, demographic and baseline characteristics, prior and concomitant medications, and exposure will be based on GSK Core Data Standards. Details of the planned displays are presented in [Appendix 12: List of Data Displays](#).

### 6.2. Display Details

#### 6.2.1. Participant Disposition

##### Participant Status and Reason for Study Withdrawal

The number and percentage of participants who completed the study as well as participants who withdrew from the study will be summarized by participant status and reason for withdrawal. The number of participants who completed the study for purpose of the disposition table will consist of all randomized participants who, as documented in the eCRF, Study Conclusion form, have completed all study periods through the Day 57 visit. This table will also include those subjects who entered washout but were never randomized.

A listing of reasons for study withdrawal will be provided for all participants who were withdrawn from the study. This listing will include treatment, site ID, unique subject ID, date of withdrawal, study day of withdrawal, primary reason for withdrawal from study, was a follow-up phone contact attempted 3 times, and was a follow-up certified letter mailed.

##### Treatment Status and Reasons for Discontinuation of Study Treatment

A summary of the number and percentage of participants who completed the study treatment as planned, as well as participants who stopped study treatment prematurely will be produced.

A listing of the randomized treatment discontinuation record will be provided for all participants who prematurely discontinued randomized treatment. This listing will include treatment, site ID, unique subject ID, date of last dose, study day of discontinuation, primary reason for discontinuation, and sub reasons for discontinuation, and related to study treatment.

##### Participant Disposition at Each Study Period

The number and percentage of participants who entered, withdrew from and completed screening, washout, HGB maintenance Period, and follow-up of the study will be summarized by treatment group and overall.

**CONFIDENTIAL**

205665

Pre-Protocol Amendment 3	Post-Protocol Amendment 3
Study Period (Visit)	Study Period (Visit)
Screening* (Week -8 to Week -4)	Screening* (7-30 days prior to Week -2)
ESA Washout* (Week -4 to Day 1)	ESA Washout* (Week -2 to Day 1)
Hgb Maintenance Phase (Day 1 to Day 57)	Hgb Maintenance Phase (Day 1 to Day 57)
Follow-up (Day 58 to Week 10)	Follow-up (Day 58 to Week 10)

\*For these visits, the period will include the first visit up to but not including the last reference visit. For example, screening period for pre-protocol amendment 3 will be defined as week -8 up to but not including the week -4 visit.

#### Screening Status and Reasons for Screen Failure

The number and percentage of participants who passed screening (i.e. enrolled) and who failed screening and therefore were not entered into the study will be summarized along with the reasons for failure will be summarized for those participants who failed screening. If a subject has been screened multiple times, the subject's latest screening information will be displayed. (Note that the reasons for rescreen participants who initially failed but subsequently enrolled are not included in the display.)

A listing of the screen failure record for all participants who failed screening and were not enrolled in the study will be produced. This listing will include site ID, unique subject ID, date of screen failure, reason term(s) for screen failure (including the specify text, if any).

#### Number of Participants by Site ID

The number and percentage of participants by Site ID will be summarized by treatment group and overall for the Enrolled population.

A listing of planned and actual treatments will be provided. This listing will include site ID, unique subject ID, randomization number, randomization date, randomized treatment, actual treatment and deviation.

### **6.2.2. Protocol Deviations**

#### Important Protocol Deviations

The number and percentage of participants who had important protocol deviations (defined in protocol deviation management plan) will be summarized by category and by treatment group and overall.

**CONFIDENTIAL**

205665

A listing of important protocol deviations will be provided. The listing will include treatment, site ID, unique subject ID, date of deviation, study day of deviation, protocol deviation category, protocol deviation coded term, and protocol deviation description.

Participants with Inclusion/Exclusion Criteria Deviations

The number and percentage of participants who had inclusion/exclusion criteria deviations will be summarized by inclusion/exclusion type, criteria description and by treatment group and overall.

A listing of participants with inclusion/exclusion criteria deviations will be provided. The listing will include treatment, site ID, unique subject ID, inclusion/exclusion type, and criteria description.

### **6.2.3. Population Analysed**

Study Populations

The number and percentage of screened participants in the Screened, Enrolled, Safety, ITT, PP, PK will be summarized by treatment group and overall.

Exclusion from Safety Population

The number and percentage of participants excluded from the Safety population will be summarized by reason, treatment group and overall in individual displays for each study population.

A listing of participants excluded from the Safety population will be provided. The listing will include the treatment arm, site ID, unique subject ID, date of deviation, study day of deviation, category, coded term and criteria which lead to exclusion.

### **6.2.4. Demographic and Baseline Characteristics**

Demographic Characteristics

Demographic and baseline data will be summarized by treatment group and overall for ITT, Safety, and PP populations. PP only to be produced if used in sensitivity analysis.

A by-subject listing of demographic and baseline characteristics will also be produced. This listing will include treatment, site ID, unique subject ID, year of birth, age, sex, ethnicity, height, weight, and other demographic and baseline characteristics.

Age Ranges

A summary of age ranges will be produced based on the Enrolled population.

### Race and Racial Combinations

Summaries of race and racial combinations will be produced for each treatment group and overall.

A listing of race details by participant will also be produced, which will include treatment, site ID, unique subject ID, race, and race detail.

## **6.2.5. Medical Conditions, Prior and Concomitant Medications**

### Medical Conditions

A summary of baseline medical conditions will be provided by treatment group and overall.

A listing of medical conditions will be produced, which will capture both pre-specified medical conditions and other medical conditions collected on the eCRF.

### Concomitant Medications

For reporting purposes, medications will be classified as prior (pre-treatment), concomitant (on-treatment), and post-treatment using the associated start and stop dates recorded in the eCRF and relative to the first and last dose dates of IP (see Section 14.4.1). Medications will be coded using the GSK Drug coding dictionary (current version at the time of DBR).

The number and percentage of participants reporting the use of each concomitant medication will be summarized by GSK-Drug Anatomical Therapeutic Chemical (ATC) classification level 1, 2, 3 (body system) and ingredient. Drugs that are composed of a combination of ingredients will be displayed according to the ATC classifications of the ingredients, not of the combination. Summaries of pre-treatment, on-treatment, and post-treatment medication will be provided separately. See Section 14.4.1.1 for a summary of study phases for concomitant medications.

A listing of all medications taken by participants, including any of which are only prior or post-treatment, will be produced. The relationship between ATC level 1, 2, 3, and ingredients and verbatim text for all medications in the study will be listed.

## **6.2.6. Exposure and Treatment Compliance**

Months (or days) of exposure (see Section 14.6.2) will be summarized using mean, standard deviation, minimum, P25, median, P75, and maximum by treatment group and overall.

A listing of exposure data will be provided. This listing will include treatment, site ID, unique subject ID, dose start date, dose stop date, duration of time on dose, dose, dose units, dose form, route of administration, and dosing frequency.

**CONFIDENTIAL**

205665

Summary of percent compliance will be summarized using mean, standard deviation, minimum, P25, median, P75, and maximum.

A listing of compliance data will be provided. This listing will include treatment, site ID, unique subject ID, and percent compliance.

Compliance is only calculated for Daprodustat because rhEPO subjects are dosed at site.

## **7. EFFICACY ANALYSES**

### **7.1. Primary Efficacy Analyses**

Efficacy is not evaluated for this study. The primary objective is Pharmacodynamic, the average systolic blood pressure (SBP) over 6-hr post-dosing after 8 weeks, this is described in Section [11](#).

## 8. SAFETY ANALYSES

The safety analyses will be based on the Safety population, unless otherwise specified.

Objectives	Endpoints
Safety	

 
To assess the safety and tolerability of daprodustat
 
	
 
Incidence and severity of adverse events (AEs) and serious adverse events (SAEs)
 
Reasons for discontinuation of study treatment
 
Absolute values and changes from baseline over time in laboratory parameters, electrocardiograms (ECGs) and vital signs
 

### 8.1. Adverse Events Analyses

Adverse events analyses including the analysis of AEs of special interest (AESI), adverse events (AEs), Serious (SAEs) and other significant AEs will be based on GSK Core Data Standards. The details of the planned displays are provided in [Appendix 12: List of Data Displays](#).

#### *Adverse Events*

The number and percentage of participants reporting at least one AE will be provided for each treatment group. These events will be summarized by treatment group, primary system organ class, and preferred term. Pre-treatment, post-randomization, treatment emergent and follow-up AEs will be summarized separately, specifically the on treatment AEs will be separated by acute challenge 1, HGB maintenance, and acute challenge 2. HGB maintenance is defined as the dates between acute challenge 1 and 2.

Summaries of all AEs will be produced for the safety population.

A listing of AE records for all participants who reported AEs will be produced.

The number and percentage of participants reporting the most common treatment emergent AEs (those occurring in  $\geq 2\%$  of participants in any treatment group) will be summarized by preferred term and treatment group. Rounding is not applied, e.g. with a threshold of 2% then a preferred term occurring in 1.99% of subjects would not be included.

The number and percentage of participants reporting treatment emergent AEs assessed by the investigator to be related to the study drug will be summarized by treatment group, primary system organ class, and preferred term and separately by overall frequency.

The number and percentage of participants and the number of occurrences of common non-serious treatment emergent adverse events will be summarized by primary system organ class, preferred term, and treatment group and separately by overall frequency.

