5.4. Screening/Baseline/Run-in Failures

Screen failures are defined as subjects who consent to participate in the clinical trial but who never enter the washout period. In order to ensure transparent reporting of screen failure subjects, meet the Consolidated Standards of Reporting Trials (CONSORT) publishing requirements, and respond to queries from Regulatory authorities, a minimal set of screen failure information is required including Demography, Screen Failure details, Eligibility Criteria, and Serious Adverse Events (see Section 7.3.1.6).

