7.3.1.1. Time Period and Frequency for Collecting AE and SAE Information

- Any SAEs assessed as related to study participation (e.g., protocol-mandated procedures, invasive tests, or change in existing therapy) or related to a GSK product will be recorded from the time a subject consents to participate in the study up to and including any follow-up contact.
- AEs will be collected from the start of washout until the follow-up contact (see Section 7.3.1.3), at the timepoints specified in the Time and Events Table (Section 7.1).
- Medical occurrences that begin prior to the start of washout but after obtaining informed consent may be recorded on the Medical History/Current Medical Conditions section of the CRF.
- All SAEs will be recorded and reported to GSK within 24 hours, as indicated in Section 12.4. The investigator will submit any updated SAE data to the sponsor within 24 hours of it being available.
- Investigators are not obligated to actively seek AEs or SAEs in former study subjects. However, if the investigator learns of any SAE, including a death, at any time after a subject has been discharged from the study, and he/she considers the event reasonably related to the study treatment or study participation, the investigator must promptly notify GSK.

NOTE: The method of recording, evaluating and assessing causality of AEs and SAEs plus procedures for completing and transmitting SAE reports to GSK are provided in Section 12.4.

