### 4. ANALYSIS POPULATIONS

Population	Definition / Criteria	Analyses Evaluated
Screened	
 
All participants who were screened for eligibility
 
	
 
Screen Failures
 

Enrolled	
 
All participants who enter washout.
 
Participants will be analyzed according to the treatment to which they were randomized, if randomized.
 
	
 
Study Population, Safety
 

Safety	
 
All randomized participants who received at least one dose of study treatment.
 
This population will be based on the treatment the participant actually received.
 
Note: Participants who were not randomized but received at least one dose of study treatment should be listed.
 
	
 
Safety
 

Intent-To-Treat (ITT)	
 
All randomized participants [who received at least one dose of study treatment].
 
This population will be based on the treatment the participant was randomized to.
 
Any participants who receives a treatment randomization number will be considered to have been randomized.
 
	
 
Primary, secondary, and exploratory endpoints excluding PK endpoints
 

Per-Protocol (PP)	
 
All participants in the ITT population who comply with the protocol.
 
Protocol deviations that would exclude participants from the PP population are defined in Section 4.1 (Protocol Deviations) and Appendix 1: Protocol Deviation Management and Definitions for Per Protocol Population.
 
	
 
Sensitivity analysis of primary endpoint
 

CONFIDENTIAL

205665

Population	Definition / Criteria	Analyses Evaluated
	
 
The PP set will not be analysed if this population comprises more than 90% of the ITT population.
 
	
Pharmacokinetic (PK)	
 
All participants in the Safety population who had at least 1 non-missing PK assessment (Non-quantifiable [NQ] values will be considered as non-missing values).
 
	
 
All PK endpoints
 

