**14.4.2. Treatment Emergent Flag for Adverse Events**

All AEs (non-serious AEs and serious AEs) will be collected and recorded on the eCRF from the start of treatment, including washout period, until the follow-up visit at the time points specified in the SoA from [Appendix 2](#). Serious AEs assessed as related to study participation (e.g., study treatment, protocol-mandated procedures, invasive tests, or change in existing therapy) or related to a GSK product will be recorded on the eCRF from the time a participant consents to participate in the study up to and including any follow-up contact.

Treatment State	Definition
Pre-treatment	
 
For participants with a non-missing screen failure date, if AE onset is on or before the screen failure date: AE Start Date <math>\leq</math> Screen Failure Date
 
For randomized participants with a missing treatment start date, all AEs are considered pre-treatment
 
For randomized subjects with a non-missing treatment start date, if AE onset date is before treatment start date: AE Start Date <math><</math> Treatment Start Date
 

Post-randomization	If AE onset date or AE worsening date is on or after the randomization date Randomization date $\leq$ AE Start Date Randomization date $\leq$ AE Worsening Date
Treatment emergent	If AE onset date or AE worsening date is on or after treatment start date & on or before the last non-zero dose date plus 1 day. Treatment Start Date $\leq$ AE Start Date $\leq$ Last Non-Zero Dose Date + 1 day Treatment Start Date $\leq$ AE Worsening Date $\leq$ Last Non-Zero Dose Date + 1 day
Follow-up	If AE onset date or AE worsening date is after the last non-zero dose date plus 1 day. AE Start Date $>$ Last Non-Zero Dose Date + 1 day AE Worsening Date $>$ Last Non-Zero Dose Date + 1 day
Onset /Worsening Time Since 1 st Dose (Days)	If Treatment Start Date $>$ AE Onset Date = AE Onset Date - Treatment Start Date + 1 If Treatment Start Date $\leq$ AE Onset Date = AE Onset Date - Treatment Start Date + 1 If Treatment Start Date $>$ AE Worsening Date = AE Worsening Date - Treatment Start Date If Treatment Start Date $\leq$ AE Worsening Date = AE Worsening Date - Treatment Start Date + 1 Missing otherwise.

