**CONFIDENTIAL**

205665

ICH: Listings					
No.	Population	IDSL / Example Shell	Title	Programming Notes	Deliverable
Prior and Concomitant Medications					
10.	ITT	CM10	Listing of Concomitant Medications	IDSL	DR, SAC
11.	ITT	CM6	Relationship between ATC Level 1, 2, 3, Ingredient and Verbatim Text	IDSL	DR, SAC
Exposure and Treatment Compliance					
12.	Safety	EX3	Listing of Exposure and Treatment Compliance Data	ICH E3, include % treatment compliance for each subject	DR, SAC
Adverse Events					
13.	Safety	AE8	Listing of All Adverse Events - Safety	ICH E3	DR, SAC
14.	Enrolled	AE8	Listing of All Adverse Events - Enrolled	ICH E3	DR, SAC
15.	Safety	AE7	Listing of Subject Numbers for Individual Adverse Events	ICH E3	DR, SAC
16.	Safety	AE2	Listing of Relationship Between Adverse Event System Organ Classes, Preferred Terms, and Verbatim Text	IDSL	DR, SAC
Serious and Other Significant Adverse Events					
17.	Safety	AE8	Listing of Fatal Serious Adverse Events	ICH E3	DR, SAC
18.	Safety	AE8	Listing of Non-Fatal Serious Adverse Events	ICH E3	DR, SAC
19.	Safety	AE14	Listing of Reasons for Considering as a Serious Adverse Event	ICH E3	DR, SAC
20.	Safety	AE8	Listing of Adverse Events Leading to Withdrawal from Study / Permanent Discontinuation of Study Treatment	ICH E3	DR, SAC
Hepatobiliary (Liver)					

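### The pre-treatment AE and SAE tables cover only randomized, dosed subjects, so events in subjects who stop during the ESA washout are listed but not counted

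*SAP*

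**What the plan says.** - **Collection.** Protocol 7.3.1.1: "AEs will be collected from the start of washout until the follow-up contact".
- **Populations.** SAP 4 defines Enrolled as "All participants who enter washout" and lists its use as both study population and safety analyses. It defines Safety as "All randomized participants who received at least one dose of study treatment".
- **Default for safety.** SAP 8: "The safety analyses will be based on the Safety population, unless otherwise specified". SAP 8.1 repeats this for adverse events: "Summaries of all AEs will be produced for the safety population". The same section plans separate summaries of pre-treatment, post-randomization, treatment-emergent and follow-up events, for AEs and again for SAEs.
- **Displays.** In SAP 14.12.5 every AE and SAE table names the Safety population. In SAP 14.12.11, Listing 14 is the one AE display on the wider set: "Listing of All Adverse Events - Enrolled".
- **Treatment state.** The first of three pre-treatment rules in SAP 14.4.2 reads "For participants with a non-missing screen failure date, if AE onset is on or before the screen failure date". The other two are for randomized subjects, with and without a treatment start date.
- **Screen failures.** Protocol 5.4: "Screen failures are defined as subjects who consent to participate in the clinical trial but who never enter the washout period".

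**The concern.** The washout is imposed by the trial: subjects stop their ESA for 2 weeks, with a further week possible if Day 1 hemoglobin is high. Subjects who entered before Amendment 3 had a washout from Week -4. Protocol Table 2 provides for withdrawal on Day 1 before any dose, and SAP 14.6.1 and 14.6.2 contain derivations for subjects withdrawn in washout, so the plan allows for such losses.

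Having chosen to summarize pre-treatment events, the SAP does so in a set defined by what happened afterwards. An event serious enough to end participation before dosing takes the subject out of both numerator and denominator. The pre-treatment columns could then be read as a description of the washout when they describe only those who completed it and were dosed. What is at stake is the completeness of a descriptive safety summary, not the comparison of daprodustat with epoetin alfa.

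**Working it through.** No power or error-rate figure bears on this point. The check is a reading of the population attached to each display.

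**1. Who is in which set.** A subject who enters washout and is withdrawn before randomization is in Enrolled and not in Safety. A subject randomized but never dosed is also in Enrolled and not in Safety.

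**2. Which tables are involved.** The AE and SAE tables are 2.1 to 2.13 (13 tables), 2.24 (1) and 2.30 to 2.34 (5), so 13 + 1 + 5 = 19. All 19 use Safety and none uses Enrolled. The programming notes give a pre-treatment section to only four: 2.1, 2.10, 2.12 and 2.24. Tables 2.3 to 2.9 are treatment-emergent and Table 2.2 covers the treatment phases, so a dosed set is right for those.

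**3. Following one subject.** Take a subject who has an SAE during washout and is withdrawn before randomization.

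| Display | Population | Does the event appear? |
|---|---|---|
| Tables 2.1, 2.10, 2.12, 2.24, pre-treatment section | Safety | No |
| Listing 13, all AEs | Safety | No |
| Listing 14, all AEs | Enrolled | Yes |
| Listings 17 and 18, fatal and non-fatal SAEs | Safety, treatment-emergent only (8.1) | No |
| Table 1.1 and Listing 2, withdrawal and its reason | Enrolled | Withdrawal only, no AE count |
| Table 1.3, disposition by period | Screened | Withdrawal only, no AE count |

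If the same SAE occurs in a subject who goes on to be dosed, it is counted in the pre-treatment sections.

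**4. The treatment state.** Rule one in 14.4.2 needs a screen failure date, and by Protocol 5.4 someone who entered washout is not a screen failure. Rules two and three need randomization. A subject who entered washout and was never randomized meets none of them. A note in 14.4.2 also sends an event with missing onset and resolution dates to treatment-emergent and post-randomization, with no exception for a subject who was never randomized. Rule two, by contrast, does give a state to randomized subjects without a treatment start date. SAP 14.6.2 treats those subjects as having zero exposure, so they fall outside Safety and the rule cannot affect the tables as planned.

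**5. Size.** The documents give no number lost in washout. From the planned 124 screened and 62 randomized, screen failures and washout losses together are 124 - 62 = 62, so the washout group is at most about that and could be far smaller. For scale only, if a fraction L of entrants is lost, reaching 62 randomized means 62/(1 - L) - 62 lost:

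- L = 5%: 65.3 - 62 = 3.3
- L = 10%: 68.9 - 62 = 6.9
- L = 20%: 77.5 - 62 = 15.5

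These rates are assumptions with no source in the documents, and they count subjects, not events.

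**The case against.** The strongest reply is that nothing is lost. Listing 14 shows every AE in every enrolled subject, serious and fatal ones included. Table 1.1 expressly takes in subjects who entered washout and were never randomized, SAP 8.4 cites it as a safety output, Listing 2 gives the reasons, and Table 1.3 counts entry to, withdrawal from and completion of washout. All of this stands. A reader might infer that washout harm is under-reported, or that every AE table uses the wrong population. The documents support neither: the events are listed but not summarized, and only four tables have a section where the wider set matters.

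A reader might also infer that a washout death would be missing from the fatal SAE listing because of the population. That misplaces the cause. SAP 8.1 limits Listings 17 and 18 to treatment-emergent events, so a washout SAE is out of scope even for a subject later dosed, and changing the population alone would add nothing.

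The safety objective concerns daprodustat, and undosed subjects cannot inform a comparison of arms. That stands for treatment-emergent and follow-up events. It does not settle the pre-treatment sections, which are not about drug effect and which the SAP chose to produce.

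Lastly, the protocol itself points to low risk. In earlier studies, 4 weeks on placebo gave a mean hemoglobin fall of 0.61 to 0.72 g/dL with no subject meeting the stopping criterion or needing rescue (Protocol 4.4), and one of the Day 1 withdrawal routes is high hemoglobin. This is fair, and it is why no size of harm is claimed here. The gap in 14.4.2 has little effect on Listing 14, which needs no treatment state, but it would matter once these subjects are tabulated.

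**Conclusion.** The point holds in a limited form. The planned pre-treatment AE and SAE counts in Tables 2.1, 2.10, 2.12 and 2.24 are conditional on getting through washout and being dosed, although SAP 4 already defines a population without that condition and gives it a safety use. SAP 14.4.2 leaves subjects who entered washout but were never randomized without a treatment state. The number of subjects and events involved is unknown and may be small. The conclusion rests on the population column of the display list and on the Protocol 5.4 definition of screen failure, not on any assumed loss rate. It is an inexpensive correction to a descriptive summary.

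**What to change.** 1. Produce the pre-treatment sections of Tables 2.1, 2.10, 2.12 and 2.24 on the Enrolled population, with an added 'not randomized' column. Keep Safety for treatment-emergent and follow-up events.
2. Add to the pre-treatment definition in SAP 14.4.2: 'enrolled participants who were never randomized or never dosed: all AEs are pre-treatment', and let this take precedence over the missing-date note.
3. Cite Listing 14 in SAP 8.1, which mentions an AE listing without naming the Enrolled set.
4. If Listings 17 and 18 are meant to show washout SAEs, change both their population to Enrolled and their treatment-emergent scope in 8.1. Changing one without the other has no effect.

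The cost is SAP wording, one extra column and a few changed displays. The data are already collected, and subject care, the primary analysis and the treatment comparison do not change.
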